### **3.2 Type of trial**

This is an open label, randomised, multiple dose, cross-over relative bioavailability and pharmacokinetics trial of oral 13–CRA liquid administered to patients aged from 0-< 21 years. The decision to initiate 13-CRA therapy will be taken independently of this trial protocol. The trial will be conducted in patients who are attending the hospital for treatment for neuroblastoma requiring at least two cycles of 13-CRA. 13–CRA will be prescribed to patients according to the locally approved treatment protocols at a dose of 200mg/m^2/day for both test and reference product. Oral 13–CRA is administered for NBL (this is usually at a dose of 160mg/m^2) for 14 days, every 4 weeks, for 6 months, however where the dose is extracted from capsules this dose

is increased to 200mg/m^2. In this trial the dose of 13-CRA will be 200mg/m^2 as patients able to swallow the capsules will not be recruited to the trial. Patients with a body weight of ≤12kg will receive a dose of 160 mg/m^2. Patients who require their dose through a nasogastric tube or gastromy will be included in the trial, this will be recorded in the case record form.

When an appointment is made for the patient to attend the hospital clinic for initiation of 13-CRA treatment the parent(s)/legal guardian of the patient will be approached to discuss the pharmacokinetic trial and the possibility of the patient's entry into the trial; information regarding the trial may be sent to parents and patients prior to them attending. The parent(s)/legal guardian's consent to take these additional blood samples and record physiological information (local [oro-pharyngeal] tolerability, skin toxicity, adverse events) will be sought. Following parental consent, the patient will be approached and the trial procedures explained to them in order to receive their verbal and/or written assent to participate in the trial, if applicable (usually where the patient is over 7 years of age). Parents and patients may still refuse to participate in the trial at any stage prior to or during their treatment with 13-CRA. Parents and patients will be given as much time as they need to consider participation in the trial. Patients and parents may choose to share information about the research with their family or GP before they decide if they would like to take part in the trial. Investigators will ensure that families have at least 24 hours to consider involvement in the trial. In practice this is likely to be longer as parents and patients are most likely to be approached well in advance of their 13-CRA treatment period. If the parent(s)/legal guardian decide that they would not like their patient to participate in the trial then this will in no way affect the onward care of the patient.

When the patient attends hospital for initiation of 13-CRA treatment, it is anticipated that they will have a central line *in situ*. Patients will attend the clinic on Pharmacokinetic days; these will be Day 1 and Day 14 for each of the trial treatment periods. Blood samples for pharmacokinetic analysis will be taken over the course of six hours after which the patients will leave the clinic. Parents and patients will be asked if they are willing to return for an additional sample at 24-48 hours following their final dose on Day 14 of treatment.

Additional assessments will be made according to the trial procedures (section 4).

[figure not shown]
A trial schedule is presented in Appendix I.

### **3.3 Expected duration of patient participation**

Patients will be administered twice-daily doses of 13-CRA for the duration of the trial. Evaluation of the test and reference product will occur over two months of therapy. Individual patient's participation will therefore be 2 months, including a two-week follow-up.

### **3.4 Trial schematic and schedule**

A trial schematic for individual patients is presented in Figure 3.4 and a full schedule is presented in Appendix I.

**Figure 3.2 Trial Schematic for an individual**

### 3.5 Data to be recorded on the case report form

The following data will be recorded on the patient's case report form:

- Unique patient identifier- to identify site and patient number in trial.
- Date of informed consent (and receipt of assent if applicable).
- Demographic data: age, gender, race.
- Weight and height.
- Vital signs: blood pressure, temperature, heart rate (supine pulse rate) and respiratory rate.
- Physical examination.
- Safety laboratory results (taken as part of routine standard care of the patient, relevant results will be recorded in the CRF)
- Relevant non-oncology medical history: relevant past medical history in the four weeks prior to the trial, known allergies and relevant longstanding conditions that are on-going.
- Oncology history (diagnosis) and treatment (over the last month) to include concomitant medication for their indication (i.e. confirmation of eligibility for 13-CRA treatment and current treatment).
- Concurrent medication: any non-oncology medication taken in the month prior to trial.
- Inclusion/exclusion criteria.
- Concomitant medications taken during participation in the trial.
- Dose of 13-CRA (equally divided doses, and daily timing of doses on the trial diary card) – including calculation of body surface area and daily dose required.
- Confirmation of randomisation number, test/or reference treatment and batch numbers.
- Time of treatment.

- Precise time of blood sampling.
- Details of any local oro-pharyngeal tolerability (recorded as adverse events if appropriate). Oro-pharyngeal tolerability will be assessed before and after dosing. Any oro-pharyngeal adverse events will be recorded on the trial diary card.
- Palatability. This will be assessed at Day 14 in the clinic using a palatability questionnaire that will be completed by the patient/patient's parents (depending on the age of the patient).
- Adverse events – all events occurring during the timeframe of the trial and for a period of 14 days afterwards (on the trial diary card).
- Serious adverse events – all events regarded as serious during course of trial and until resolution.
- Trial withdrawal information, if applicable.
- Date and time of trial discharge (i.e. when the patient completes the period of follow up).

## **4. TRIAL PROCEDURES**

### **4.1 Demography**

The following demographic characteristics will be recorded at the visit: age, sex, race, height, weight.

### **4.2 Medical History**

Oncology history and treatment will be recorded to confirm eligibility. Additional relevant medical history during the four weeks prior to the trial will be recorded. This will include all current conditions by diagnosis (where possible) and any concomitant medication.

### **4.3 Physical Examination**

A qualified medical practitioner will carry out a general physical examination. This will involve an external examination of the cardiovascular, respiratory and gastro-intestinal systems. This will be performed at baseline prior to treatment to ensure no concurrent conditions exist that may exclude the patient from the trial.

### **4.4 Safety Laboratory Assessments**

Measurement of the haematological and biochemical parameters will be carried out prior to each course of 13-CRA treatment in line with standard of care. Additional and/or more frequent clinical assessments and laboratory tests may be carried out at the discretion of the investigator in line with standard of care. Safety laboratory tests will not be undertaken as part of the trial protocol, however results of routine laboratory tests may be collected as part of the safety assessment of the two treatment periods. Any findings that the investigator considers to be an adverse event\* will be recorded on the case record form (specifically for the following parameters):

- Full blood count including haemoglobin, white blood cell, neutrophil, lymphocyte and platelet counts.
- Renal and liver function (Na, K, Ca, Mg, PO4, urea, creatinine, glucose, total protein, bilirubin, transaminases)
- Serum lactate dehydrogenase (LDH)

\* Abnormal laboratory values or test results will generally constitute adverse events only if they induce clinical signs or symptoms or require therapy, although investigators may report any laboratory finding or test result that they consider to be clinically relevant.

#### 4.5 Pregnancy Prevention

For women of childbearing potential all conditions of the Pregnancy Prevention Programme should be met (8). Patients of childbearing potential, their partners and parents must understand and accept the need for effective contraception, be informed and understand the potential consequences of pregnancy and the need to rapidly consult if there is a risk of pregnancy. Female patients of childbearing age must be provided with comprehensive information on pregnancy prevention and should be referred for contraceptive advice if appropriate. As part of the standard clinical care, female patients of childbearing potential will undergo a pregnancy test no more than seven days prior to the start of treatment and routinely no more than seven days before each course of treatment. Although the likelihood of pregnancy in patients receiving 13-CRA is extremely low, if a positive pregnancy test does result during the trial, the next course of treatment will not be given until the pregnancy has been discussed with the treating clinician, and the patient will be withdrawn from the trial whether or not treatment is continued.

#### 4.6 13-CRA Dosing and Blood sampling for Pharmacokinetic analyses

All patients recruited into the trial will already have a central line *in situ*.

Patients will receive their first morning dose of 13-CRA according to standard practice (for capsules by extracting the medicine from the capsule), or according to liquid dosing instructions, and will include a drink of water (volume to be included in dosing instructions) after dosing. Dosing instructions (including which foods such as yogurt or ice cream can be given with the medicine) for both medicine extracted from capsules and liquid will be provided to the site in a separate dosing manual, this document will be version controlled and retained in the trial files at site.

The pharmacokinetic profile of 13-CRA post dosing will be evaluated.

At least five blood samples (2ml) will be (where possible) taken post-dose at the time-points specified in Table 4.6 below. In patients under two years of age, up to three samples at appropriate sampling times will be taken. Sampling times in the patients under 2 years of age will be discussed with the Sponsor prior to the trial PK sampling days in order to ensure an even spread of sampling times in this younger population of patients. Arrangements will be discussed and agreed in writing (or by email) on an individual basis for this group.

**Table 4.6 Blood Sampling Schedule**

Time point (h)	Requirements
0.5 (Day 1 and Day 14)	*Two and six hour samples are mandatory.  At least three further samples will be selected over 0.5 to 5 hours (where possible).  **Sample at 24-48 hours applies only to the final dose administered on Day 14 to allow the elimination phase of parent and metabolite(s) to be calculated. For individual patients sampling times should remain the same across each of the four PK days, where possible.
1	
1.5	
2	
3	
4	
5	
6	
24-48 (Day 15 or 16)	

Flushing of the central line with normal saline and allowance for dead space will be performed according to local practice.

2.0 ml blood samples will be taken and processed immediately according to the technical manual and laboratory kit provided to the trial staff. This technical manual will be version controlled and retained in the trial files at site

#### **4.7 Vital Signs**

At baseline an assessment of vital signs will be made: Systolic and diastolic blood pressure, pulse and body temperature at baseline (in older patients this will be following 5 mins rest in supine position). Following dosing vital signs will be monitored according to routine standard of care, any unexpected measurements will be recorded as adverse events and reported in the normal way.

#### **4.8 Palatability assessments**

At the end of each of the two treatment cycles patients (together with their parents) will be surveyed using a standard questionnaire for their views of the palatability and acceptability of the 13-CRA. In the case of patients <6 years of age, the researcher will survey the view of one or both parents. For patients from 6 years of age, the researcher will seek the views of one or both parents and the patient.

The questionnaire will probe the taste and general acceptability (willingness to continue with treatment, ease of dose administration etc.). After five patients have completed the survey the use of the questionnaire will be reviewed, by both the investigator and Nova, to ensure that it is working satisfactorily. If the questionnaire needs to be adjusted (in terms of its administration or the ability/age groups of the patients), then this will be done. Minor amendments only will be made. All minor edits will be documented and a copy of the amended questionnaire will be provided to the Ethics Committee. If significant adjustment is required Ethical Committee Approval will be sought before administering the amended questionnaire.

Data on the following will be collected using a visual (hedonic) analogue scale and verbal responses.

- Taste on first administration
- Residual after taste
- Smell
- Any incidences of spitting medicine out or vomiting
- Willingness to take 13-CRA on a daily basis
- Ease of dose administration using the bottle and oral syringe
- Preference between extracted capsule and liquid medicines

The survey will be conducted by a trained research nurse. The survey will be face to face with patient and/or parent and will be conducted on Day 14 of each treatment cycle and take no longer than 5 minutes. In addition aspects of palatability may be included in the patient diary card if appropriate. Diary cards will be provided to the Ethics Committee for approval prior to use.

#### **4.9 Tolerability assessments**

All adverse events will be collected and recorded during the trial and for the 14 day follow up period. Patients and parents will be provided with a trial diary card and will be asked to record adverse events.

Common adverse events associated with 13-CRA include dry or peeling skin, cracked lips and dry eyes, skin may also become more sensitive to sunlight. Therefore these adverse events collected during the trial will be separately listed.

13-CRA can cause some mild changes in liver function and hypercalcemia, therefore standard of care laboratory assessments will be made to monitor liver function and serum calcium levels.

#### 4.10 Oropharyngeal Tolerability

Oro-pharyngeal tolerability and symptoms will be separately assessed. Dry skin, peeling skin, cracked lips and dry eyes will be assessed by the investigator on a four point scale (0 = none, 1 = mild, 2 = moderate, and 3 = severe).

Oro-pharyngeal symptoms will be assessed at baseline and following administration of 13-CRA during the Pharmacokinetic Day 14. Patients and parents will be provided with a diary to record any oro-pharyngeal events during the two weeks treatment. This diary card will be reviewed and discussed with the parents (and patient if appropriate) on Day 14 for each of the treatment cycles. Any local clinically relevant changes will be recorded as adverse events, classified by type of event (e.g. lesion, and/or other) and severity.

### 5. SELECTION OF PATIENTS

Up to 20 patients will be enrolled into the trial depending on the number of pharmacokinetic blood samples that are obtained from each patient. A minimum of 150 pharmacokinetic blood samples are required for adequate analysis of the patient population.

To ensure each age cohort is appropriately represented by age the trial will aim to include a minimum number of patients to the following age groups:

Age 1 - <2 years: 4 patients  
Age 2 - < 6 years: 4 patients

#### 5.1 Inclusion criteria

To be eligible for inclusion into this trial the patients must fulfil all of the following criteria:

1. Male or female aged from 0 years to < 21 years of age.
2. Patient with high risk neuroblastoma, or unresectable, unfavourable histology intermediate risk neuroblastoma the latter age  $\geq$  18 months at diagnosis
3. Patient who is scheduled to receive at least two treatment cycles of 13-CRA.
4. Patient who cannot swallow 13-CRA capsules (i.e. requires extraction of 13-CRA from the capsules).
5. Negative pregnancy test for females of childbearing potential no more than seven days before initiation of treatment, and sexually active patients and partners agreeing to undertake adequate contraceptive measures (see section 4.5).
6. Provision of a single or double lumen central venous catheter for sampling (i.e. already in place).
7. Parent(s)/legal guardian able and willing to provide written informed consent for the patient to take part in the trial.
8. Where applicable, the patient should assent to undergo blood sampling for pharmacokinetic purposes and to allow physiological measurements to be made.

#### 5.2 Exclusion criteria

To be eligible for inclusion in this trial the patients must **not** meet any of the following criteria:

1. Any clinically significant medical condition or abnormality, which, in the opinion of the investigator, might compromise the safety of the patient or which might interfere with the trial.
2. Diagnosis of high-risk neuroblastoma (HRNBL) which is currently being treated on the SIOPEN HRNBL trial (patients who have exited this trial will be eligible).
3. Known allergy to 13-CRA or any of the excipients.
4. Inadequate contraception measures in females of childbearing age.
5. Receiving concomitant treatment with tetracyclines.

## 5.2 Criteria Prior to starting each cycle of 13-CRA

1. Total bilirubin  $\leq 1.5$  x normal, and (SGPT) ALT  $\leq 5$  x normal. Veno-occlusive disease if present, should be stable or improving.
2. Skin toxicity no greater than CTCAE Grade 1
3. Serum triglycerides  $< 5.65$  mmol/L.
4. No haematuria and / or proteinuria on urinalysis.
5. Serum calcium  $\geq 2.0$  mmol/L to  $\leq 2.9$  mmol/L.
6. Serum creatinine based on age / gender as follows:

Age	Maximum Serum Creatinine $\mu$ mol/L	
	Male	Female
1 month to $< 6$ months	35	35
6 months to $< 1$ year	44	44
1 to $< 2$ years	53	53
2 to $< 6$ years	70	70
6 to $< 10$ years	88	88
10 to $< 13$ years	106	106
13 to $< 16$ years	132	124
$\geq 16$ years	150	124

7. Patients with a seizure disorder must be well controlled and taking anticonvulsants. CNS toxicity  $<$  grade 2 (CTCAE).

## 5.3 Withdrawal criteria

Parent(s)/legal guardian and patients may withdraw from the trial at any time without their care being affected and continue on existing route of 13-CRA administration for remainder of cycles.

1. Positive pregnancy test - pregnancy testing will be undertaken no more than seven days before treatment commences and routinely no more than seven days before each course of treatment in females of childbearing potential. If a patient is found to be pregnant during the trial, the next course of treatment will not be given until the pregnancy has been discussed with the treating clinician, and the patient will be withdrawn from the trial whether or not treatment is continued.
2. Request of the patient, for any reason.
3. Discretion of the investigator.

# 6 TREATMENT OF PATIENTS

## 6.1 Evaluation of test and reference treatment

Evaluation of the test and reference product will occur during two months of the therapy only.

Consent to take part in the trial will be obtained before any trial procedures are undertaken.

Patients who are already receiving 13-CRA treatment will also be eligible for the trial, so long as they are able to commit to two cycles of trial 13-CRA. The next planned 14-day treatment cycle will be classed as My-CRA Month 1. After consent to take part has been obtained and prior to the initiation of the next 14 day treatment patients will be randomised to receive either 13-CRA liquid (test product) or liquid extracted from capsule (reference product) in My-CRA Month 1. Randomisation will be done once eligibility has been confirmed and their next scheduled treatment visit is booked, in order that the appropriate medication can be made available for the

patient's visit. Randomisation will be done centrally by Nova according to a randomisation list generated by the trial statistician, investigators will email (or telephone) Nova to receive randomisation details, this will be confirmed by email as "liquid first" or "extracted capsules first", pharmacy contacts will also be notified. After My-CRA month 1, patients will then cross over to the alternative formulation in My-CRA Month 2. In all other treatment cycles patients will revert to standard therapy i.e. liquid extracted from capsules. The pharmacokinetics of 13-CRA will be evaluated during test and reference treatments (My-CRA Month 1 and 2).

## **6.2 Permitted medications**

Concomitant medication is defined as any medication, other than the trial drug, which is taken during the trial (i.e. before the patient completes the 14 day follow up visit after My-CRA cycle 2), including prescription and over-the-counter medicines.

For the purposes of the trial, nutritional supplements including vitamins and minerals are not considered concomitant medications, although vitamin A supplements will not be allowed (according to standard practice). The generic names of medications should be used where possible. Concomitant medication will be recorded in the CRF with indication, dose information, and dates of administration. Any new medications taken or any changes to the form, frequency or dose of existing medication occurring during the trial will also be recorded. The use of concomitant medications is based upon the experience of the clinical investigator.

## **6.3 Monitoring compliance**

Medication will be prescribed and dispensed by the pharmacy. On pharmacokinetic days (Day 1 and 14) morning doses of medication will be administered in the clinic. All additional doses of medication will be recorded fully on the patient's diary card. Prescription, dispensing and accountability of 13-CRA will be accurately recorded in the drug accountability log provided by the Sponsor. The trial monitor will verify that the data have been accurately recorded and transferred.

## **6.4 Exit points**

The normal exit point from this trial will be when the patient completes the 14 day follow up visit in My-CRA month 2, all adverse events will be followed up to conclusion.

## **6.5 Expected duration of patient participation**

Patients will be in the trial for a 2 month period.

## 7 INVESTIGATIONAL MEDICINAL PRODUCT

The term 'Investigational Medicinal Product' will refer to the 13-CRA liquid administered to the patient as part of the pharmacokinetic trial.

### 7.1 Description of investigational medicinal product

Drug Substance	13-Cis Retinoic Acid
Manufacturer of Drug Product	The test drug product will be manufactured and batch released by: Nova Limited, [name].  The reference drug product will be an approved, commercial product that will be purchased by the Sponsor and supplied to the local pharmacy, the manufacturer is: Roche Products Limited, [name]. Product License: PL 00031/0160
Test Drug Product	Novel oral liquid formulation of 13-Cis Retinoic Acid
Reference Drug Product	Isotretinoin capsules-Roaccutane® 20 mg soft capsules (to be extracted per dosing instructions provided)
Daily dose	The dose administered will be 200mg/m  /day for both test and reference product. Patients with a body weight of ≤12kg will receive a dose of 160 mg/m  .
Frequency	100 mg/m  twice daily (morning and evening) for 14 days per patient
Packaging, Test Drug Product	50 ml Amber type III glass bottle with tamper evident child-resistant closure. Packaged with oral dosing syringes. Storage at room temperature (15 to 25°C) The medicinal product is photosensitive and should be protected from light and stored in the original carton at all times Shake the bottle vigorously for at least 30 seconds before use
Packaging, Reference Drug Product	Capsules, soft 10 and 20 mg capsules: Oval, opaque, brown-red and white capsules imprinted with ROA 20 in black ink. Duplex (PVC/PVDC) aluminium blister packs containing 20, 30, 50 or 100 capsules. Storage at room temperature (15 to 25°C)

The product will be prepared and dosing on the pharmacokinetic days will be by the site staff or by parents supervised by site staff, and will be according to instructions provided by The Sponsor (separate document to be version controlled). Remaining doses will be given to the patients by their parents/guardians, and will be according to instructions provided to them. Parents will be trained according to these instructions and local hospital standard procedures.

13-CRA dosing will be prescribed by qualified medical personnel.

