## 1. INTRODUCTION

### **The need for a liquid formulation**

Neuroblastoma (NBL) is an aggressive cancer that predominantly affects children aged 5 years or less. It is an orphan disease (incidence ~ 10 cases per million children; 1 case per 500,000 general population) that still has poor outcomes.

Children who present with metastatic NBL (approximately 50% of cases) are most commonly treated with myelo-ablative chemotherapy followed by stem-cell rescue and, to eradicate 'minimal residual disease' post rescue, 13-cis-retinoic acid (13-CRA, isotretinoin) usually alongside immunotherapy. Given by the enteral route, at a dose of 80 mg/m^2 twice daily, in 2-week cycles for 6 months 13-CRA has been shown in clinical trials to improve event-free survival. Thus, most clinicians accept 13-CRA as frontline therapy for patients with NBL in remission.

However, 13-CRA is not licensed for NBL in any region or country in the world and is currently available only as a gelatin capsule that children are often unwilling and / or unable to swallow. Presently, carers have to 'open' capsules of 13-CRA, and squeeze the contents into foods. As few young children will take capsules, carers often have to administer 13-CRA by first extracting liquid out of the capsule. Studies show that the current method of administration results in marked variability in drug exposure between patients and significantly lower plasma concentrations in patients receiving the extracted drug as compared to those able to swallow the capsules whole (1). Furthermore, since 13-CRA can cause birth defects, pregnant women (e.g. parent of a child with NBL) risk accidentally exposing their unborn babies when extracting 13-CRA from capsules.

No manufacturer has yet developed a child-friendly preparation of 13-CRA. Nova Laboratories Limited is developing a new oral liquid dosage form of 13-CRA, which will facilitate more consistent and accurate dosing and improve palatability for children.

This trial aims to investigate the relative bioavailability and comparative pharmacokinetics of the new oral liquid and existing capsule formulations of 13-CRA in patients. Any patient requiring at least two treatment cycles with 13-CRA will be eligible for the trial. The local oropharyngeal tolerability, the palatability and acceptability of the formulation will also be assessed.

The trial will be conducted in compliance with the protocol, ICH GCP and the applicable regulatory requirement(s).

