### 7.3 13-CRA dosing

The appropriate dose will be delivered to each patient, according to the weight of the patient to deliver approximately 200 mg/m^2 13-CRA. Patients with a body weight of ≤12kg will receive a dose of 160 mg/m^2.

Each patient enrolled in the trial will receive 13-CRA in accordance with the dosing requirements.

Initial doses will be administered and checked by trained medical/nursing staff and recorded accurately in a controlled drug accountability log provided by the Sponsor. Remaining doses will be recorded by the parents/guardians in the diary card.

The Sponsor monitors will check the accuracy of the pharmacy and site for receipt of IMP, confirmation of receipt, pharmacy storage of the IMP packages, distribution records to the clinic and records of return to pharmacy and destruction of IMP. Any anomalies will be queried and clearly documented. All records will be maintained in the hospital pharmacy files with anonymised copies retained for the Sponsor trial master file.

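### For patients of 12 kg or less, adjacent rows of the Section 7.1 product table give daily doses that differ by 25%, and no section states their amount per administration

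*Protocol*

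**What the plan says.** Two adjacent rows of the Section 7.1 table matter here.

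- **Daily dose row.** It opens with the general dose, "The dose administered will be 200mg/m"² per day for both products. It then sets the low-weight rule, "Patients with a body weight of ≤12kg will receive a dose of 160 mg/m"², with no time unit attached.
- **Frequency row.** It gives 100 mg/m² "twice daily (morning and evening) for 14 days per patient". No weight band is mentioned.

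The low-weight sentence recurs without a time unit on the title page, in the synopsis (Dose and Treatment strategy), in Sections 1.1.2, 3.2 and 7.3, and in SAP sections 3 and 6. Section 7.3, the section devoted to dosing, says the dose is set "according to the weight of the patient to deliver approximately 200 mg/m"² and then repeats the low-weight figure. Neither figure has a time unit there. Section 3.2 gives the general dose once per day and later without a unit: "In this trial the dose of 13-CRA will be 200mg/m"².

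Other sections give context. The introduction describes the usual regimen: "Given by the enteral route, at a dose of 80 mg/m"², twice daily. Section 3.2 says of the usual neuroblastoma dose that "this is usually at a dose of 160mg/m"², raised to 200 mg/m² when the drug is extracted from capsules. Section 3.3 and the synopsis state twice-daily dosing for all patients, and Section 3.5 has the case report form record the daily dose split into equal parts.

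**The concern.** The Frequency row holds the only per-administration amount that the protocol states for trial dosing. Someone writing or checking a twice-daily order would naturally turn to it. For a child of 12 kg or less, following it literally departs from the low-weight rule one row above.

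The documents themselves show why this matters. The introduction describes a target concentration range of 2 to 10 µM, more frequent toxicity above 10 µM, and dosing that is not adjusted to blood levels. A discrepancy in the prescribed dose would therefore not be corrected through drug-level monitoring.

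Section 7.6 asks the investigator to keep records showing that patients received the protocol's dose. SAP section 8 lists non-compliance with the investigational product as a major deviation, which can remove a patient from the pharmacokinetic population. Neither can be judged consistently for a weight band whose dose is stated in two conflicting ways.

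**Working it through.** The check is arithmetic on the stated doses. No sample-size or power figure is involved.

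**Inputs**

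- General dose: 200 mg/m² per day (Section 7.1, Daily dose row).
- Low-weight dose: 160 mg/m², no time unit (same row).
- Frequency: 100 mg/m², twice daily, 14 days (Section 7.1, Frequency row).
- Usual regimen: 80 mg/m² twice daily (introduction).
- Two administrations per day for all patients (Section 3.3), equally divided (Section 3.5).

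**Step 1: reproduce the plan's own figures.** Daily dose = amount per administration × 2.

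- Frequency row: 100 × 2 = 200 mg/m² per day. This agrees with the general dose.
- Introduction: 80 × 2 = 160 mg/m² per day. This agrees with the usual dose in Section 3.2 if that figure is a daily total.

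**Step 2: apply both rows to a patient of 12 kg or less.** Cycle total = daily dose × 14.

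| Source | Per administration (mg/m²) | Per day (mg/m²) | Per 14-day cycle (mg/m²) |
|---|---|---|---|
| Daily dose row, read as a daily total in two equal parts | 160 / 2 = 80 (derived, not stated for this band) | 160 | 160 × 14 = 2240 |
| Frequency row, as written | 100 | 200 | 200 × 14 = 2800 |

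Ratio: 200 / 160 = 1.25. The Frequency row gives 25% more than the Daily dose row. The difference is 2800 − 2240 = 560 mg/m² per cycle.

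**Step 3: look for a passage that resolves it.** None of the places where the low-weight sentence recurs gives an amount per administration. The Frequency row has no footnote or exception. The 80 mg/m² in the introduction describes the usual regimen and is not tied to this weight band.

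**The case against.** The strongest reply is that the intention can be inferred. The 160 mg/m² figure stands in a row labelled Daily dose. The introduction and Sections 3.2, 3.3 and 3.5 fit a daily total given in two equal parts. The exception is printed one row above the Frequency row, and the sponsor's separate dosing instructions, which are not among the documents, may state the amount. The chance of an actual dosing error is therefore unknown.

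Much of this stands. It shows that the missing time unit is a lesser defect than the clash between the rows. It also disposes of two stronger readings that a reader might infer.

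- **A third reading.** Because the 160 mg/m² has no time unit, a reader might take it as the amount at each of two administrations, which is 160 × 2 = 320 mg/m² per day. The documents do not support this. The row label contradicts it in Section 7.1, and elsewhere it requires an unlabelled sentence, such as the one in Section 7.3, to be read without its context.
- **Bias in relative bioavailability.** A reader might infer that the ambiguity undermines the equal-dose basis of the comparison. Each child receives both formulations, and the same dose wording covers both. Bias would arise only if a child's two periods were dosed differently, and nothing in the documents suggests that. Doses given are also recorded on the case report form, the diary card and the accountability log (Sections 3.5, 6.3 and 7.3), so a difference would be visible.

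The reply does not remove the conflict between the two rows. Context may suggest what was meant, but the Frequency row still says something else, and Section 7.6 makes the protocol the reference for checking doses. A separate manual does not correct the protocol's own text.

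**Conclusion.** The point holds as an internal inconsistency between two rows of one table. For patients of 12 kg or less, Section 7.1 gives 160 or 200 mg/m² per day, a 25% difference, and no section states their amount per administration. The missing time unit on the 160 mg/m² sentence adds to the problem, but it does not create a further reading that the documents support.

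The 25% assumes that the 160 mg/m² is a daily total, as its row label indicates. The number of patients affected is not known. The documents give no weight distribution, so it could be anything from none to all of the up to 20 planned. The trial seeks at least 4 patients in its youngest age group, but how many of them weigh 12 kg or less would be an assumption.

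This must be corrected, because it concerns the dose given to the smallest children. That rating rests on the conflict between the two rows alone. Nothing here says which figure is right.

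**What to change.** Reconcile the Daily dose and Frequency rows of Section 7.1 with each other, and bring the title page, the synopsis, Protocol Sections 1.1.2, 3.2 and 7.3 and SAP sections 3 and 6 into line. At each place, every weight band should show one figure, its unit (per day or per administration) and the number of administrations per day. The separate dosing instructions should be checked against the reconciled text. The sponsor's clinical team must settle the figures.

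The cost is a wording amendment, with the written ethics approval that Section 12.4 requires before an amendment is implemented. No analysis, sample size or assessment schedule changes.
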